1.5.1 Efficacy Endpoints

- OS from the time of Cycle 1, Day 1 of immunotherapy until death from any cause.
- MFS from the time of Cycle 1, Day 1 of immunotherapy until first documented distant metastases on imaging or death, whichever occurs first.
- LPFS from the time of Cycle 1, Day 1 of immunotherapy until first documented local progression on imaging or death, whichever occurs first.
- Surgical resectability determined by successful performance of resection (as defined by R0 and R1 resection).
- Pathologic response as determined by surgical margins and residual disease.

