1.7 Study Design

This is a single-center, open label, phase I/II clinical trial to evaluate the immune effects, safety and clinical activity of the combination of nivolumab and CCR2/CCR5 dual antagonist with or without GVAX in patients who have received standard chemotherapy and stereotactic body radiation therapy (SBRT) for LAPC.

Patients who have a new diagnosis of untreated LAPC will be eligible for enrollment. We will consent patients at the time of diagnosis of LAPC based upon criteria from NCCN Guidelines as determined by review of imaging and pathology at our institution. If the patient has not had a diagnostic core biopsy adequate for review by our institution, an on-study core diagnostic biopsy will be performed. If the patient's available imaging is not adequate for review by our institution, repeat imaging will be performed. The patient will also undergo blood draws at the time of screening and enrollment. After completing all screening procedures and meeting eligibility criteria, the patients will then receive FOLFIRINOX-based induction chemotherapy and SBRT. Chemotherapy and radiotherapy are considered standard therapy. Chemotherapy may be administered at any facility, but SBRT treatment will be performed at Johns Hopkins. Of note, patients should meet all eligibility criteria and have all screening procedures completed prior to initiating chemotherapy, however they may be enrolled up to one month after beginning SOC chemotherapy to allow for time to collect records from outside institutions if necessary. Only toxicities considered related to study procedures or treatment will be collected during this period. The patients should receive at least eight and no more than sixteen 14-day cycles of FOLFIRINOX-based chemotherapy. After completion of chemotherapy, the patients will undergo EUS-guided fiducial placement along with a post-chemotherapy core biopsy of the pancreas tumor, blood draws to evaluate for circulating tumor cells and other inflammatory markers and an SBRT simulation. We will not confirm presence of tumor in the post-chemotherapy core biopsy since some patients may not have persisting tumor; the biopsy is to evaluate the tumor microenvironment. SBRT will be initiated (6.6 Gy x 5 days) approximately two to four weeks after completion of chemotherapy.

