After completion of SBRT, the patients will then be re-evaluated for eligibility for continuation in the study and must have LAPC based on NCCN Guidelines as determined by review of CT, PET, or MRI imaging at our institution. Patients who have developed metastatic disease are no longer eligible to continue in the study. If the patients remain eligible for continuation in the study after rescreening, they will be assigned or randomized to a study arm (depending on when they were enrolled).

Due to availability of BMS-813160, study enrollment was closed as of December 19, 2022. Patients randomized prior to this will continue receiving study treatment as planned until drug supply expires on July 31, 2023, then will continue to receive any remaining study cycles without BMS-813160. Any patients who were enrolled but not randomized prior to December 19, 2022 (i.e. those receiving chemotherapy) will be assigned to a new arm (Arm C).

In phase I, the combination immunotherapy consists of nivolumab, CCR2/CCR5 dual-antagonist (BMS-813160) and GVAX. In phase II, the first 10 patients will be randomized 1:1 between Arm A and Arm B. Remaining patients will be assigned to Arm C.

Arm A subjects receive nivolumab and BMS-813160, Arm B subjects receive nivolumab, BMS-813160, and GVAX, and Arm C patients will receive nivolumab and BMS-813160 for Cycle 1 (prior to surgery) and then nivolumab and GVAX for Cycles 2 and beyond.

After randomization or assignment to a study arm, subject will receive Cycle 1 of the combination immunotherapy. Cycle 1 lasts 28 days and will start within two weeks of completion of SBRT.

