9. STUDY SCHEDULE

Patients will be evaluated and consented at the time of initial diagnosis of LAPC. Patients should meet all eligibility criteria and complete all screening procedures prior to starting SOC chemotherapy, however they can be enrolled up to one month after initiating SOC chemotherapy to allow for time to gather all records from outside institutions if necessary. Patients will then receive 8-16 14-day cycles of FOLFIRINOX-based chemotherapy, followed by SBRT between 2-4 weeks after completion of chemotherapy. Both chemotherapy and radiation therapy are standard therapies for LAPC, and will be administered off-trial. They will have another evaluation for eligibility to receive immunotherapy after completion SBRT at which point they will be randomized during Phase II and they will initiate Cycle 1 Day 1 of combination immunotherapy within 2 weeks of completion of SBRT. The patient will undergo Post-Immunotherapy Evaluation within one week after Cycle 1 Day 28.

Pre-surgical Study Schedule						
Procedure	Screening/ Baseline	Pre-Immunotherapy Screening (within 3 weeks prior to C1D1)	Cycle 1 Immunotherapy (within 2 weeks after completion of SBRT)			End of Cycle 1 (day before surgery or C1D28, whichever is earlier) ²⁴
			C1D1 ²	C1D2 ³	C1D15 ⁴	
Visit Window ¹ (days)			-	-	+3	-3/+14
Nivolumab (All patients)			X			
GVAX (Phase 1 and Arm B patients)				X		
BMS-813160 (All patients) ⁵			X	X	X	X
Eligibility criteria	X	X				
Randomization (Phase 2 only) ⁶		X				
Demographics	X					
Medical History ⁷	X	X				
Medications	X	X	X		X	X
Physical Exam ⁸	X	X	X			X
Vital Signs and pulse ox ⁹		X	X	X	X	X
Height ⁹		X				
Weight		X	X		X	X
Performance Status	X	X	X		X	X
EKG for PR, QRS and QTcF ¹⁰		X	X		X	X
Hematology profile ^{11, 12}	X	X	X		X	X
Chemistry profile ^{11, 13}	X	X	X		X	X
TSH ^{11, 14}		X	X			X
Serum/Urine Preg ^{11, 15}	X	X	X			
CA 19-9 ¹¹	X	X	X			X
Urinalysis and microscopic exam ^{11, 16}		X				
INR ¹¹		X				
HLA-Typing ¹¹			X			
Adverse event evaluation		X	X		X	X
Vaccine Site Assessment						X
PET-CT, CT, or MRI ¹⁷	X	X				X ¹⁸
Tumor measurements ¹⁷	X	X				X ¹⁸
Pathology Review	X	X				
Peripheral blood for research (up to 100cc) ¹⁹			X			X
Serum (20cc) ¹⁹			X			X
Plasma (20cc) ¹⁹			X			X
Archival Tissue ²⁰	X					
EUS Core Biopsy ¹⁹		X ²¹				X ²²
QoL Questionnaire ²³			X			X

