12.6 Analysis of Secondary Endpoints – Efficacy Assessment

The secondary endpoints of interest are OS, MFS and LPFS, which are defined as the time from the study treatment initiation until death, evidence of metastatic disease or local

A Phase I/II trial of combination immunotherapy with nivolumab and a CCR2/CCR5 dual antagonist (BMS-813160) with or without GVAX following chemotherapy and radiotherapy for locally advanced pancreatic ductal adenocarcinomas (PDACs)

progression, respectively. The evaluable populations for OS, MFS and LPFS includes all subjects who receive at least one dose of study drugs (nivolumab, BMS-813160, or GVAX), and there will be a subgroup analysis for those who complete one cycle of study combination immunotherapy. If a patient is lost to follow-up, withdraws from the study or dies prior to being diagnosed with metastatic disease or local progression, or the study is ended prior to death, the patient will be considered censored at their last recorded follow-up. Kaplan-Meier survival curves will be constructed and the median survival estimates will be calculated with 95% confidence intervals using Greenwood's formula. Survival curves will be compared to historical data using log rank test. Because the study sample size is not powered for comparing the OS and MFS, comparisons with historical data will be performed for explorative purpose. Proportions of surgical resectability and pathologic response will be reported along with the corresponding binomial exact 95% confidence intervals.

Other secondary endpoints include surgical resectability and pathologic response. Surgical resectability will be determined by review of imaging and review of the subject's surgical candidacy (clinical status and tumor status) off trial after the patient completes off-trial chemotherapy and radiotherapy. Pathologic response will be graded after surgical resection or biopsy with comparisons of pre-and post-immunotherapy core biopsies or surgical samples. For each outcome, the proportion will be calculated with an exact 95% confidence interval. Individuals who drop out of the study due to treatment toxicity or other causes prior to outcome assessment will be counted as not resectable and non-responders. Logistic regression will be used to assess the impact of risk factors on each outcome. Time to event analyses will be used to assess the timing of resection and response.

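### Section 12.6 judges surgical resectability by candidacy review at an unclear time, whereas the endpoint in 1.5.1 is a performed R0/R1 resection; pathologic response is also defined in two ways

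*Combined protocol and SAP*

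**What the plan says.** **Resectability.** Section 1.5.1 (Efficacy Endpoints) reads: "Surgical resectability determined by successful performance of resection (as defined by R0 and R1 resection"). Section 12.6 reads: "Surgical resectability will be determined by review of imaging and review of the subject's surgical candidacy (clinical status and tumor status"), with the review placed "off trial after the patient completes off-trial chemotherapy and radiotherapy". For this endpoint 12.6 mentions neither immunotherapy nor an R0/R1 result. The same paragraph counts patients who drop out before assessment, through toxicity or another cause, as not resectable, and plans time-to-event analyses of when resection occurs.

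**Timing elsewhere.** Section 9 says: "Both chemotherapy and radiation therapy are standard therapies for LAPC, and will be administered off-trial". Section 1.7 starts Cycle 1 within two weeks of the end of SBRT and schedules surgery five to seven weeks after SBRT. Footnotes 17 and 18 of the pre-surgical schedule put the surgical-evaluation imaging after immunotherapy and before planned surgery. Sections 1.7 and 9 provide for candidates who turn out to be unresectable during the operation.

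**Pathologic response.** Section 1.5.1: "Pathologic response as determined by surgical margins and residual disease". Section 12.6: "Pathologic response will be graded after surgical resection or biopsy with comparisons of pre-and post-immunotherapy core biopsies or surgical samples".

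**Objectives.** Objectives 1.2.5 and 1.2.6 ask for both rates in patients who go on to receive the immunotherapy, compared with historical controls.

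**The concern.** A secondary endpoint should have one numerator, one assessment time and one denominator. Here an analyst who follows 12.6 reports a different quantity from the one the endpoint section names. Being judged a candidate and having had an R0/R1 resection are different outcomes, and the protocol itself provides for patients who have the first without the second.

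The time point matters as well. An assessment made after chemoradiotherapy but before study drug would describe the effect of standard treatment, not of the immunotherapy in objective 1.2.5.

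For pathologic response, a patient who is not resected has no surgical margin. Such a patient can be graded under 12.6 but not on the margin component of 1.5.1.

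The trial is open-label and single-center, and both rates are meant for comparison with historical controls. An unsettled definition leaves room to choose the numerator once the results are known.

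**Working it through.** The documents give no sample size or power for either endpoint. Their only related figure is the 30-40% of patients expected to be resected (section 1.7). The check is therefore mainly a comparison of texts.

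**1. Criterion for resectability**

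| Patient | 1.5.1 | 12.6 |
|---|---|---|
| R0/R1 resection performed | counted | counted, if judged a candidate |
| Judged a candidate, found unresectable at operation | not counted | counted |
| Judged not a candidate | not counted | not counted |
| NanoKnife procedure without resection | not counted (no R0/R1 result) | not stated |
| Drops out before assessment | not counted | not counted (explicit rule) |

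The second row is a direct contradiction and does not depend on when the review takes place.

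**2. Assessment time**

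- Cycle 1 starts 0 to 2 weeks after SBRT, and surgery follows 5 to 7 weeks after SBRT.
- Surgery therefore falls between 5 − 2 = 3 and 7 − 0 = 7 weeks after study drug begins. A performed resection is always an outcome after exposure to study drug.
- A review tied only to the end of chemoradiotherapy is not so constrained. It could fall in the interval of up to two weeks before Cycle 1 Day 1.

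**3. Size, resectability**

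Let N be the patients, C those judged candidates and R those with an R0/R1 resection. If every resected patient was judged a candidate, the rates are C/N under 12.6 and R/N under 1.5.1, and they differ by (C − R)/N.

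One patient classified differently moves the rate by 1/N. Section 12.2 plans 8 to 10 patients in Group 1. For Group 2 it says up to 10, but its components give 6 + 5 = 11. So 1/11 = 9.1 and 1/8 = 12.5 percentage points. These group sizes come from the plan for the primary endpoint; 12.6 does not say which groups it reports.

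Illustration with N = 10 and exact 95% intervals, the interval type that 12.6 specifies:

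| Count | Rate | Exact 95% CI |
|---|---|---|
| 3 resected | 30% | 6.7% to 65.2% |
| 4 resected | 40% | 12.2% to 73.8% |
| 6 candidates (assumed) | 60% | 26.2% to 87.8% |

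With R = 3, the difference for C = 3, 4, 5 or 6 is 0, 10, 20 or 30 points. The candidate count is an assumption throughout, because the documents do not give one. If the review took place before study drug, a patient not then a candidate could later be resected, and the difference could go either way.

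**4. Pathologic response**

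With 30-40% resected, 100 − 40 = 60% to 100 − 30 = 70% are expected to be unresected. These are the patients whom 12.6 can grade from a biopsy and who have no margin for 1.5.1. The conflict concerns criterion and population. It does not concern timing, since 12.6 names post-immunotherapy samples here.

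**5. Denominator**

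Section 12.6 defines an evaluable population for OS, MFS and LPFS, but none for these two proportions. The drop-out rule settles part of the question only.

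**The case against.** The strongest reply is that 12.6 was never meant to describe an assessment before immunotherapy. It does not say so: completion of chemoradiotherapy sets only an earliest time. The toxicity drop-out rule and the planned analysis of resection timing both fit an assessment after study treatment. Footnotes 17 and 18 place the surgical evaluation after Cycle 1. The term off trial may only reflect that surgery is standard of care. This reply stands as far as it goes: the assessment time is ambiguous, not demonstrably wrong. It does not remove the conflict between candidacy review and performed resection, which remains on either reading.

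A reader might go further and infer that the 12.6 rate is close to zero by design, because patients continuing after SBRT "must have LAPC based on NCCN Guidelines as determined by review of CT, PET, or MRI imaging at our institution". The documents do not support this. It requires the early reading, and the protocol's own expectation that 30-40% will be resected suggests that reading was not intended.

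A reader might also infer that the protocol admits to biopsy cores without tumour, and hence to false pathologic responses. What it says is "We will not confirm presence of tumor in the post-chemotherapy core biopsy since some patients may not have persisting tumor". That describes possible true absence of tumour in a patient after chemotherapy. It reports no sampling error, and no misgrading rate can be derived. The 60-70% figure shows who could be graded by biopsy, not who would be graded wrongly.

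Finally, 1/N per patient is a feature of any binary endpoint in groups this small, and no powered test or sample size depends on these endpoints. Both points are fair and limit the weight of the concern.

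**Conclusion.** The concern holds in this form. Followed as written, 12.6 yields a different resectability rate from the endpoint in 1.5.1 whenever a candidate proves unresectable at operation, and its time point is ambiguous. Pathologic response is defined on margins and residual disease in one place and on grading that includes biopsies in the other.

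The size is 9.1 to 12.5 percentage points per patient classified differently, if the rates are reported in groups of 8 to 11. The total shift cannot be derived, because the documents give no count of candidates who are not resected. The example of 60% against 30-40% rests on an assumed six candidates in ten.

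The importance is moderate. Both endpoints are secondary and unpowered, and the primary immunologic endpoint and the safety rules are unaffected. Correction is still worthwhile, because objectives 1.2.5 and 1.2.6 set these rates against historical controls.

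**What to change.** In 12.6:

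- **Resectability.** Replace the candidacy-review sentence with an R0/R1 resection performed at the surgery following Cycle 1. Use all patients who start Cycle 1 Day 1 as the denominator. Count patients not explored, found unresectable at operation, or dropped out before surgery as not resected. State how a NanoKnife procedure without resection is counted.
- **Pathologic response.** Reconcile with 1.5.1. Report the margin and residual-disease endpoint on resection specimens, with unresected patients as non-responders in the all-treated rate. Report biopsy-based changes separately. Restricting the endpoint to resection specimens is partly a choice; its merit is that it agrees with 1.5.1.

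The cost is wording in the analysis section. It needs no new data collection and changes no surgical or treatment decision. The downside is that reported rates may be lower: with unresected patients as non-responders, the all-treated pathologic response rate cannot exceed the share resected, which the protocol expects to be 30-40%.

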12.7 Exploratory Analysis – Quality of Life

Quality of life will be assessed via EORTC QLQ-C30/Pan26 (v3.0) questionnaire. Our study population is pancreatic cancer subjects, and the analysis will be focused on Global Health Status/QoL scale, symptom scale (fatigue, pain), and functional scale (physical functioning, role functioning, emotional functioning) comparing data from initial enrollment into study and as per study calendar (**Section 9**). For each module, summary statistics of the score will be reported as baseline and follow up time. Changes of quality of life score before and after treatment will be tested via paired t-test. In addition, mixed effect models will be fitted for assessing the pattern of quality of life over time. The frequency and proportion of patients who reach minimal clinically important difference (MCID) of 10-points change from baseline will be tabulated by time. Logistic mixed effects models will be used to track the proportion over time. The time to definitive deterioration in quality of life, defined as a decline of 10 points or more, will be analyzed using the Kaplan Meier method.

12.8 Exploratory Analysis - Biomarkers

Pre-treatment core tumor biopsies will be taken and compared to post-treatment surgically resected or core biopsy samples. Results will be compared with those from the ongoing neoadjuvant clinical trials of GVAX+/-nivolumab for resectable PDA and of SBRT/GVAX/pembrolizumab for locally advanced PDA. Correlative studies will be done in HBIC scientific programs. Tumor infiltrating immune cells including T cells and myeloid

A Phase I/II trial of combination immunotherapy with nivolumab and a CCR2/CCR5 dual antagonist (BMS-813160) with or without GVAX following chemotherapy and radiotherapy for locally advanced pancreatic ductal adenocarcinomas (PDACs)

cells and expression of PD-L1/PD-1 and other immune checkpoints will be analyzed by the Perkin-Elmer-Vectra multiplex immunofluorescent staining in collaboration with [name] and [name] Labs. CCR2/CCR5/CXCR4 associated pathways will be analyzed by NanoString. TCR clonality assays will be done in collaboration with the [name] lab. MANAFEST assays will be done in collaboration with the [name] lab.

Potential relationships between biomarker data and efficacy or safety endpoints will be investigated as part of an analysis plan aimed at identifying baseline biomarkers that may be used to prospectively identify subjects likely (or not likely) to respond to combination nivolumab, GVAX, and BMS-813160 and to identify subjects who may be predisposed to having adverse reactions to treatment. These exploratory predictive biomarker analyses will be completed with biomarkers measured in blood and in tumor samples and will focus on factors outlined in the exploratory objectives. Similar analyses will be completed with peripheral blood samples. We will also explore standard protein biomarkers such as CA19-9 and other exploratory circulating biomarkers. The evaluable population includes all subjects.

Continuous variables will be summarized with means or medians and standard deviations. Dichotomous and categorical variables will be summarized using proportions with exact 95% confidence intervals and counts, respectively. Summaries for both pre and post administration of each immunotherapy will be computed. Plots will be used to show the changes in immune response over time.

Comparison in pre- and post-treatment biomarker data will be compared using paired t-tests (or Wilcoxon signed rank tests if appropriate) and McNemar's tests for dichotomous or categorical variables. Associations between immune parameters will be explored graphically (e.g. scatterplots, boxplots) and numerically (e.g. correlations, Fisher's exact tests). Mixed effects models will be used to assess the patterns in biomarkers over time.

Efficacy measures will include OS, MFS, LPFS, surgical resectability and pathologic response. Demographic and case-history factors will be examined to determine whether stratification or adjustments should be made within the subsequent statistical analyses, and if necessary, the appropriate stratification or adjustment will be made. Biomarkers will be summarized graphically as they relate to efficacy and safety endpoints, as applicable. Summary statistics will be tabulated. The relationships between binary measures (e.g. response) and time to event outcomes (e.g. OS) and candidate biomarkers will be investigated using logistic regression and Cox proportional hazards regression, respectively. Associations will be summarized in terms of point and interval estimates of hazard ratios, odds ratios, or other statistics, as appropriate for the analyses completed. Models to predict clinical activity based on combinations of biomarkers may also be investigated.

REFERENCES

2. Ahlgren JD. Epidemiology and risk factors in pancreatic cancer. *Semin Oncol*. 1996;23(2): 241-50.
3. Loehrer PJ, Sr., Feng Y, Cardenes H, et al. Gemcitabine alone versus gemcitabine plus radiotherapy in patients with locally advanced pancreatic cancer: an Eastern Cooperative Oncology Group trial. *J Clin Oncol*. 2011;29(31): 4105-12.

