12.2 Sample Size/Accrual Rate

Each year, approximately 250 patients with newly diagnosed locally advanced pancreatic cancer are seen at JHH. Approximately, 50% of these patients will potentially be enrolled in clinical trials.

Phase I: 3-12 patients (3+3 design with Nivo+GVAX+BMS-813160 at two dose levels, primary endpoint - safety).

Phase II: up to 15 patients (primary endpoint - immunologic)

The first 10 patients will be randomized 1:1 into two arms:

Arm A: *nivolumab*+ *BMS-813160*

Arm B: *nivolumab*+ *BMS-813160*+ *GVAX*

Up to 5 additional patients will be assigned to Arm C: *nivolumab* + *BMS-813160* in Cycle 1

Due to the availability of BMS-813160, the enrollment of Phase II Arm A and Arm B will close early before full accrual under the original protocol. An amendment is required to change the design of the phase II portion. The analysis plan is also changed accordingly. The primary endpoint remains to be immunologic response, defined in Section 12.1 above.

The analysis will be performed separately in two groups of patients receiving either *nivolumab*+ *BMS-813160* (Group 1), or *nivolumab*+ *BMS-813160*+ *GVAX* (Group 2). Group 2 will include patients treated with the triplet regimen at the RP2D during both Phase II and Phase I portion. We expect up to 10 patients in Group 2 (including 6 treated at the 300mg dose in Phase I and 5 patients in Arm B of Phase II). A rate of immune response of 5% or lower is not considered worthy of further investigation, whereas immune response rate of at least 30% is consider worthy of further study.

Group 1 will have 8, up to 10, patients treated with the doublet regimen during Phase II (including up to 5 patients in Arm A and 3 to 5 patients anticipated to be enrolled to Arm C who receive *nivolumab* + *BMS-813160* in Cycle 1 and *nivolumab* + *GVAX* from Cycle 2 and after). It allows us to make preliminary assessment of immune response.

The probability of events under different true immune response rate is as follow:

number of responders out of 8 patients	True response rate				
	0.3	0.25	0.2	0.1	0.05
>=1	0.943	0.900	0.832	0.570	0.337
>=2	0.745	0.633	0.497	0.187	0.057
>=3	0.448	0.321	0.203	0.038	0.006
number of responders out of 10 patients					
	0.3	0.25	0.2	0.1	0.05
>=1	0.972	0.944	0.893	0.651	0.401
>=2	0.851	0.756	0.624	0.264	0.086
>=3	0.617	0.474	0.322	0.070	0.012

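### Section 12.8 seeks markers of response to the three-drug combination but pools in patients who never received the three drugs together, with no regimen term

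*Combined protocol and SAP*

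**What the plan says.** Section 12.8 states the aim of the predictive analyses: to find, among baseline biomarkers, those that identify subjects "likely (or not likely) to respond to combination nivolumab, GVAX, and BMS-813160". On the population it says: "The evaluable population includes all subjects". OS, MFS, LPFS, resectability and pathologic response are then related to candidate biomarkers by logistic and Cox regression. No arm, group or regimen covariate, interaction or by-group analysis is named. Stratification or adjustment may follow if judged necessary, but only after a look at demographic and case-history factors, and regimen is neither.

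The regimens are in section 1.7: "Arm A subjects receive nivolumab and BMS-813160, Arm B subjects receive nivolumab, BMS-813160, and GVAX", while "Arm C patients will receive nivolumab and BMS-813160 for Cycle 1 (prior to surgery) and then nivolumab and GVAX for Cycles 2 and beyond". All Phase I patients receive the three drugs. Section 12.2 gives the sizes: "Phase I: 3-12 patients", ten Phase II patients randomised 1:1 to Arms A and B, and "Group 1 will have 8, up to 10, patients treated with the doublet regimen during Phase II". Its make-up is at most five from Arm A plus an expected three to five from Arm C. For the primary immune endpoint, sections 12.2 and 12.4 keep the two regimen groups separate.

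Two other places bear on this. Section 8.2 plans to correlate post-treatment PD-1 and other lymphocyte activation markers with OS and MFS, and treats the mesothelin-specific T-cell response as a measure of response to GVAX. Sections 1.6 and 12.1 plan Cox models of immune parameters against clinical outcome.

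**The concern.** The question is about one regimen and the data come from several. Arm A never receives GVAX. Arm C receives BMS-813160 only in Cycle 1 and GVAX only from Cycle 2, so never all three drugs at once. Followed as written, section 12.8 yields a marker-outcome slope averaged over these regimens, which would be reported as evidence about the triplet.

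Two errors are possible. A marker that matters only under the triplet would look weaker than it is. A marker that differs between regimens for other reasons could pick up a difference in outcome that belongs to the regimen. Either could mislead the choice of markers for a later trial.

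**Working it through.** **Patients never given the three drugs together.** Arm A 5 + Arm C 3 = 8; Arm A 5 + Arm C 5 = 10. This reproduces the Group 1 size in section 12.2.

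**Their share of all subjects.** Share = (5 + Arm C) / (Phase I + 10 + Arm C), with Arms A and B at five each:

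| Phase I | Arm C | Total | Not on triplet | Share |
|---|---|---|---|---|
| 3 | 3 | 16 | 8 | 50% |
| 3 | 5 | 18 | 10 | 56% |
| 6 | 5 | 21 | 10 | 48% |
| 9 | 5 | 24 | 10 | 42% |
| 12 | 3 | 25 | 8 | 32% |
| 12 | 5 | 27 | 10 | 37% |

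The row with 21 is also the count at the Phase II dose: six Phase I patients at 300 mg plus 15 in Phase II. All subjects would add the lower-dose cohort. The escalation rules in section 1.7 put at least three patients there first, so six at 300 mg implies a Phase I of 9 to 12 and a share of 32% (8/25) to 42% (10/24).

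**Patients given the triplet.** Arm B 5 + Phase I 3 to 12 = 8 to 17. At the Phase II dose it is 6 + 5 = 11, although section 12.2 says up to 10.

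**Dilution.** If a marker has the same distribution in both sets, the pooled slope is about p × (triplet slope) + (1 − p) × (other slope), where p is the triplet share. With assumed slopes of 1 and 0, this gives 11/21 = 0.52 or 17/27 = 0.63. A linear-model simulation (4,000 replicates per case, unit residual SD) agrees:

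| Model | 21 patients | 27 patients |
|---|---|---|
| Marker only | 0.53 | 0.63 |
| Marker + regimen main effect | 0.53 | 0.64 |
| Marker + regimen + marker-by-regimen (triplet slope) | 1.00 | 1.00 |

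A main effect of regimen does not repair dilution. Restriction to triplet patients, or an interaction, does.

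**Confounding of baseline markers.** Regimen follows enrolment period, not randomisation, for Phase I and Arm C: 6 + 5 = 11 of 21 (52%), or 12 + 5 = 17 of 27 (63%). The same simulation was run with no marker effect and an assumed regimen effect of 1 SD:

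- Marker unrelated to regimen: pooled slope about 0, with rejection at 4.5% (21 patients) and 4.8% (27 patients).
- Marker drifting by an assumed 0.5 SD per enrolment period: pooled slope about 0.13, with rejection at 7.5% and 9.4%. A regimen term brings the slope back to about 0 and rejection to 5.2% and 4.9%.

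**Confounding of post-treatment markers.** Cox tests were simulated with 10 non-triplet and 11 triplet patients, no marker effect within regimen, and assumed regimen hazard ratios of 0.67 to 0.5. A 1 SD marker shift between regimens gave a pooled type I error of about 6% to 8%. A 1.5 SD shift gave 7% to 11% in one run (2,000 replicates) and 7.9% to 14% in another (1,500 replicates). Stratified by regimen, the error was about 5%. None of these shifts or hazard ratios comes from the documents.

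**The case against.** The strongest objection is that the quoted aim concerns baseline biomarkers. GVAX cannot move a marker measured before it is given, and among the ten patients randomised to Arms A and B a baseline marker is independent of regimen in expectation. This stands. A reader might infer that marker and regimen effects are confounded throughout section 12.8, so that its associations would be spurious. The documents do not support that: confounding needs regimen to be linked to the marker as well as to the outcome, and without that link the simulation shows no inflation. What remains is possible drift through the non-randomised Phase I and Arm C patients, and the post-treatment markers that section 8.2 relates to OS and MFS.

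A second objection is that the plan already allows adjustment. It does, but conditionally and for other kinds of factor, so following it need not lead to regimen.

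A third is that the three-drug phrase is loose wording, since section 12.8 points to the exploratory objectives and several of these say with or without GVAX. That may be so. If it is, the target sentence is what needs changing; the mismatch between target and population is there either way.

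Finally, the analysis is exploratory with no stated alpha, and the type I error figures rest on assumed effects. Both are true, and they limit how much weight the point carries.

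**Conclusion.** The point holds as a mismatch between target and population. A slope pooled over 16 to 27 patients, of whom 32% to 56% never received the three drugs together, cannot show response to the triplet. That follows from the documents' own regimens and counts. The amount of dilution depends on how far the marker effect differs between regimens: in the extreme case of an effect under the triplet only, the pooled slope is about 0.5 to 0.6 of the true one.

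Confounding is a possibility, not a finding. Where it was assumed, false-positive rates rose from about 5% to between 6% and 14%, and the upper end needs a 1.5 SD marker shift. The primary endpoint is untouched, since it is already analysed by group. This is a low-severity correction to an exploratory section, worth making because it needs only a few sentences.

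**What to change.** In section 12.8:

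- Base statements about the three-drug combination on patients who received all three drugs together (Phase I and Arm B), with the lower-dose Phase I patients identified. They belong to neither Group 1 nor Group 2, so those labels alone would leave them without a place.
- For models that use all subjects, stratify Cox models by regimen received, defined by the arm in which treatment started so that later cycles do not determine the stratum. Include regimen in the mixed models and, where the number of events allows, in the logistic models.
- Treat any marker-by-regimen term as exploratory.
- Show Arm A as the no-GVAX comparison. Pool Arm C with Arm A only for outcomes measured after Cycle 1 up to surgical evaluation. For OS, MFS and LPFS show Arm C separately, because it receives GVAX from Cycle 2; Group 1 as a whole is not a no-GVAX comparison for survival.

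This needs no new data. The cost is precision: three-drug statements would rest on 8 to 17 patients. The logistic models suffer most. With the 30% to 40% resection rate expected in section 1.7, 21 patients give 0.30 × 21 = 6.3 to 0.40 × 21 = 8.4 resections, too few to carry an extra factor comfortably. There a descriptive table by regimen may be all that is feasible.
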